- 1) Participants with a unilateral transtibial (below-knee) amputation (up to 40) will be fit with our motor-driven and computer controlled **torsionally adaptive prosthesis (TAP)**. The TAP can pair turning and flexing motion at different proportional settings; several paired motion ratio settings of turning (transverse plane motion) to flexing (sagittal plane motion) will be tested. Over two visits, participants will do a series of walking tests over level ground with the TAP set at different pairing settings (blinded and random order) while biomechanical data is collected. Satisfaction data will be collected for each setting. The results will be used to inform the design of the PFF.

Based on results from the TAP testing, we will design and build PFFs of various sizes and stiffnesses to compare to a standard-of-care prosthesis. In a blinded crossover experiment, over 3 visits, participants (up to 40) will be fit with the study prostheses (PFF or a standard-of-care prosthetic foot) in random order and wear each study prosthesis at home for 2 weeks. Participants will visit the laboratory to do a series of walking tests after each 2-week acclimation period.

List of Abbreviations

AE – adverse event

CPRS - Computerized Patient Record System

CRQ – Continuing Review Questionnaire

HIPAA – Health Insurance Portability and Accountability Act

ISO - Information Security Officer

IRB – institutional review board

PFF – Pivot-Flex Foot

PHI – protected health information

PI – Principal Investigator

PO – Privacy Officer

ROP – report of other problem

SA – specific aim

SAE – serious adverse event

SD – standard deviation

TAP – torsionally adaptive prosthesis

TT – transtibial

UW – University of Washington

VA – Veterans Affairs

Contents

Protocol Title: Pivot-Flex Foot

1.0	Key Study Personnel.....	5
2.0	Introduction.....	5
3.0	Specific Aims and Hypotheses.....	6
4.0	Resources and Personnel.....	6
5.0	Study Procedures.....	6
5.1	Study Design.....	7
5.2	Recruitment Methods and Initial Screening.....	7
5.3	Informed Consent Procedures.....	10
5.4	Inclusion/Exclusion Criteria.....	11
5.5	Study Visits, Data Collection, and Risk Management.....	11
5.6	Data Analysis.....	18
5.7	Withdrawal of Subjects.....	21
6.0	Reporting.....	21
7.0	Information Security, Privacy, and Confidentiality.....	211
8.0	Communication Plan.....	22
9.0	References.....	23

Protocol Title: Pivot-Flex Foot

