- Prosthesis information (socket, liner, suspension, and foot type, category, and/or size

Self-Selected Walking Speed (SSWS) Tests

Participants will use their own prosthesis during these tests. Participants will be asked to walk several times, at their self-selected pace, for about 65-feet back and forth in a straight hallway. Participants will also be asked to walk at their own pace several times around a ~3-foot radius circle. These tests will be used to determine each participants' straight line and circle SSWS.

Randomization to Study Prosthesis – At Home Acclimation

Participants will be randomized to wear the PFF or the standard-of-care prosthetic foot for the next 2 weeks at home/in the community during their normal daily activities. The research prosthetist will fit the PFF or standard-of-care foot to the participants as-prescribed socket and suspension system. Participants will be blinded to prosthetic foot type. The prosthetic feet will be covered with a sock and cosmesis and participants will be instructed not to remove the coverings from the foot. Participants will practice walking on the assigned foot until they feel confident/stable. If confidence and stability cannot be achieved the participant may not be able to continue in study. Participants will be instructed to contact us if they have any problems or concerns with the study prosthesis during the 2-week acclimation period. We will arrange to make prosthetic adjustments if needed. We will store the participants' prescribed prosthetic foot during the at-home acclimation periods.

Visit 2

After wearing the study prosthesis for approximately 2-weeks participants will return to the lab to do a series of walking tests.

Motion and Force Measurement

Participants will be asked to change into a tight-fitting shirt and shorts that we provide. A private changing area will be provided. We will record a series of standard body measurements such as height, weight, and leg length. We will attach up to 70 small reflective markers with double sided tape to specific locations on the participants' hands, trunk, legs, and feet.

During the walking tests in the lab, the infrared cameras will record the location and movement of the markers; they do not record a picture of the body. Data will also be collected by force plates embedded in the floor of the lab; participants will walk across and stand on the plates during the tests.

SSWS Walking Tests

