While using the study prosthesis, participants will be asked to walk back and forth in a straight line several (approximately 3-6) times at their SSWS. Participants will also be asked to walk around a ~3-foot radius circle several (3-6) times at their SSWS. They will be asked to do the circle walking tests in both clockwise and counter-clockwise directions (randomized order).

Study Prosthesis – At Home Acclimation

The research prosthetist will fit participants with the other study prosthesis. Participants will remain blinded to the foot type. Participants will practice walking on the assigned foot until they feel confident/stable. If confidence and stability cannot be achieved the participant may not be able to continue in study. Participants will be instructed to contact us if they have any problems or concerns with the study prosthesis during the 2-week acclimation period. We will arrange to make prosthetic adjustments if needed.

Visit 3

After wearing the study prosthesis for approximately 2-weeks participants will again return to the lab to do a series of walking tests. The Motion and Force Measurement, and SSWS Walking Tests described in Visit 2 will be repeated. The research prosthetist will re-fit participants with their as-prescribed prosthetic foot.

Applicable to Parts 1 & 2

During study sessions, visitors and observers will not be allowed in the lab unless the participant agrees to their presence; the participant can change her/his mind at any time.

Photos and video

We may take video and photos of participants during portions of this study for documentation and use in research publications. To protect the identity and privacy of our participants, all videos and photos will be edited later to de-identify the images (e.g., bluring of faces, tattoos, and other distinguishing marks). No sound will be recorded to prevent voice identification.

Repository

Participants will be asked if they are interested in allowing their study data to be added to our de-identified data repository so that it may be used for additional research in the future. Participants who are interested will be asked to sign a separate consent form for the repository (MIRB# 00493). Once the consent form is signed, a copy of the data will be added to the repository on an ongoing basis throughout the course of the study.

Payment to Participants

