The statistical analysis to test these hypotheses (H3.1, H3.2, H3.3, H4.1, H4.2, H4.3) will require six linear mixed effects regression analyses. These analyses will test for differences by

foot type (Pivot-Flex Foot or standard-of-care) with random effects for subject and subject by foot type interaction. The experiment-wise significance will be set a priori at an alpha level of $p<0.05$ and a Bonferroni adjustment will be applied for multiple comparisons. All analyses will be performed using existing software (R Foundation for Statistical Computing with lme4 and multcomp packages, Vienna, Austria). Exact p-values will be reported for each test.

An exploratory power analysis for peak transverse-plane moments was performed using mean values from Orendurff et al. [61] exerted by able bodied subjects performing a turning task. In Orendurff's study, subjects (n=10) completed a 270° turn around a one meter circle with a peak ankle rotational torque of 0.167 ± 0.011 Nm/kg for the inside limb. Assuming a 10% within-subject difference between study prostheses and that the standard deviations are like those of Orendurff's, there is over a 97% chance to find a significant difference between stiffness settings for 15 participants.

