Title: Pivot-Flex Foot: Optimal Coupling Ratio Between Transverse and Sagittal-plane Motions Using a Torsionally Adaptive Prosthesis for Individuals With Lower Limb Amputation

NCT03532100

Document Date: 23Sep2025

Statistical Analysis Plan

Linear mixed effects regression was used to test for an association between each outcome (dependent variable) by coupling ratio. Coupling ratio was the independent fixed effect (modeled as categorical using 4 dummy variables). Study participant and study participant by coupling ratio interaction were random effects. To address the variability in outcome variance among participants, maximum penalized likelihood estimation was used (Chung 2013). Hypothesis testing for the association between outcome and coupling ratio was carried out using conditional F-tests with degrees of freedom estimated using the Kenward-Roger method. Pairwise hypothesis testing was carried out with adjustments for multiple comparisons using Tukey's method. Results are summarized as outcome means (\pm standard error) by coupling ratio, and pairwise mean differences in outcome by coupling ratio category accompanied by standard errors and 95% confidence intervals (CI). Analyses were carried out using R 4.2.1 (Team RC, 2022), and packages tidyverse, lme4, blme and emmeans (Chung, 2013; Wickham, 2019; Bates, 2015; Lenth, 2022). Statistical analysis on satisfaction results were not performed due to the small sample size and the higher expected variances in qualitative data.

Team RC. R: A language and environment for statistical computing [Internet]. Vienna, Austria: R Foundation for Statistical Computing; 2022. Available from: www.R-project.org

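### The six Part 2 crossover models have no period term, so a common Visit 2 to Visit 3 shift widens the foot comparison and, when the sequences are unequal, biases it

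*Protocol*

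**What the plan says.** The protocol abstract describes a blinded crossover in which "participants (up to 40) will be fit with the study prostheses (PFF or a standard-of-care prosthetic foot) in random order". Section 5.5 (Part 2) gives the sequence:

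- **Visit 1:** "Participants will be randomized to wear the PFF or the standard-of-care prosthetic foot for the next 2 weeks".
- **Visit 2:** the first foot is tested, and then "The research prosthetist will fit participants with the other study prosthesis".
- **Visit 3:** "The Motion and Force Measurement, and SSWS Walking Tests described in Visit 2 will be repeated".

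Section 5.6 (Specific Aim 2) says that H3.1–H3.3 and H4.1–H4.3 "will require six linear mixed effects regression analyses". These test for differences by "foot type (Pivot-Flex Foot or standard-of-care) with random effects for subject and subject by foot type interaction". On multiplicity it says: "The experiment-wise significance will be set a priori at an alpha level of $p<0.05$ and a Bonferroni adjustment will be applied".

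No period, visit or sequence term appears in section 5.6 or elsewhere in the protocol. The SAP does not supply one: "Linear mixed effects regression was used to test for an association between each outcome (dependent variable) by coupling ratio", which is the Part 1 factor, and it contains no foot-type model. Neither document says whether the order is allocated in blocks or otherwise kept balanced.

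**The concern.** Within a participant, foot and visit change together. Anything that moves all participants between the two test sessions (familiarity with the laboratory, markers and force plates, or drift in set-up) is added to the foot difference in one sequence and subtracted from it in the other. The subject effect cancels in the within-person difference, so it cannot remove the shift. The subject-by-foot effect can only absorb it as extra variance.

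There are two consequences if a shift exists. Confidence intervals for the Part 2 contrasts are wider than they need to be. In a trial whose sequences come out unequal, part of the visit shift is reported as a foot effect. Unequal sequences can arise from simple randomisation or from withdrawals, whose data section 5.7 allows to be used.

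**Working it through.** **Inputs.** From section 5.6 (Specific Aim 2): mean 0.167 Nm/kg, SD 0.011 Nm/kg, a 10% difference (0.0167 Nm/kg), 15 participants and stated power over 97%. From section 5.1: a target of 40 for Part 2. Assumed, because the documents are silent: a Visit 3 minus Visit 2 shift π of 0, 2.5, 5 or 10% of the mean (0, 0.0042, 0.0084 or 0.0167 Nm/kg), two-sided tests, and a Bonferroni family of six (alpha 0.05/6 = 0.0083).

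**The plan's own figure.** Taking the SD of the within-person difference as 0.011 × √2 = 0.01556, a paired t-test with n = 15 has 97.1% power at 0.05. This reproduces the plan's figure, which allows for no period effect. At 0.05/6 the power is 83.9%.

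**Model.** The within-person foot difference is D = τ + π + e in one sequence (n1 participants) and D = τ − π + e in the other (n2).

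- Without a period term the estimate is the mean of D. Its bias given the split is π(n1 − n2)/n, and the variance of D gains about 4(n1/n)(n2/n)π².
- With a period term the estimate is the average of the two sequence means. It is free of π, with standard error (s/2)√(1/n1 + 1/n2) on n − 2 degrees of freedom.

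**Spread.** With equal sequences the SD of D is multiplied by √(0.01556² + 0.00835²)/0.01556 = 1.13 at a 5% shift and by 1.47 at 10%.

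**Bias, examples.** At 10:5 the bias is 5/15 × 0.00835 = 0.0028 Nm/kg for a 5% shift and 5/15 × 0.0167 = 0.0056 for a 10% shift, which are 17% and 33% of the planned effect. At 24:16 with a 10% shift it is 8/40 × 0.0167 = 0.0033.

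**Power, n = 15, alpha 0.05/6 (simulation; the 7:8 split is averaged over direction).**

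| Shift (% of mean) | Simple randomisation, without / with term | 7:8 split, without / with term |
|---|---|---|
| 0 | 84 / 79% | 84 / 83% |
| 2.5 | 81 / 79% | 81 / 83% |
| 5 | 72 / 79% | 72 / 83% |
| 10 | 42 / 79% | 39 / 83% |

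The break-even shift is about 3% of the mean under simple randomisation and 1.5–2% with a 7:8 split.

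**Type I error without the term, nominal 5%.**

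| Split | 5% shift | 10% shift |
|---|---|---|
| 8:7 | 2.8% | 0.6% |
| 10:5 | 6.3% | 6.6% |
| 11:4 | 10.4% | 17.8% |
| 20:20 | 2.6% | 0.4% |
| 24:16 | 6.3% | 6.4% |
| 25:15 | 8.6% | 11.7% |

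With the term, every entry is about 5%. Averaged over simple randomisation, the test without the term is also nominal (4.9–5.2%). If allocation is simple, a split of 11:4 or worse has probability 12% at n = 15, and 25:15 or worse has probability 15% at n = 40.

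**n = 40.** Average power without the term is about 97% or more at alpha 0.05/6 even with a 10% shift (96.6% under simple randomisation, 99.4% at 20:20). What is lost is precision. At 20:20 the 95% CI half-width is 0.00516, 0.00566 and 0.00735 at shifts of 2.5, 5 and 10%, against 0.00498 with the term, so about 4%, 14% and 48% wider.

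**Check with a mixed model.** Multi-trial data were simulated with a 10:5 split and a 10% shift, and fitted with the protocol's random effects. The mean bias was 0.0051 without the term (0.0056 expected) and about zero with it.

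**The case against.** The strongest reply is that the harm depends on a shift nobody has documented. The 10% scenario, which produces the most striking figures, makes the visit shift as large as the whole assumed foot effect. The design also works against a large shift: walking speeds are set at Visit 1, participants practise on each foot and wear it for about two weeks before testing, and Visit 3 repeats the Visit 2 procedures. Visit 2 is the first session with markers and force plates only for people who did not take part in Part 1, and the protocol allows participation in both parts.

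The planned test is unbiased with nominal type I error on average. At a 5% shift it is conservative for splits closer than 10:5 or 24:16, which are about 70% and 73% of simply randomised trials at n = 15 and n = 40. With 15 participants and simple randomisation, the term lowers power for shifts below about 3%. Finally, all the figures use one able-bodied, inside-limb torque mean and SD, so the size for straight walking, the outside limb and hip work is unknown, and the Bonferroni family of six is an inference.

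All of this stands, and it limits the weight of the point. It does not supply the missing term. Being conservative at near-equal splits is itself the loss of precision at issue, and an average over randomisations does not protect the one split that occurs.

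**Conclusion.** The point holds as an optional improvement. No Part 2 model in either document separates foot from visit. The bias formula and the added variance follow from the design whatever the size of the shift; how much they matter depends on a shift that has to be assumed. At 15 participants, a shift above about 2–3% of the mean makes the planned model less powerful than one with a period term. At 40, power is not the issue: the cost is wider intervals (about 14% at a 5% shift with equal sequences) and bias in uneven splits. If the shift is negligible, the omission does no harm. The numbers rest on the plan's torque SD with no within-person correlation, which is the reading that reproduces its stated power.

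**What to change.** In section 5.6 (Specific Aim 2), specify for all six models:

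> Fixed effects: foot type and period (Visit 2 or Visit 3). Random effects: unchanged.

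If allocation is still open, randomise the order in permuted blocks so that the two sequences stay near equal. If Part 2 outcomes have already been analysed, report the period-adjusted model as a sensitivity analysis beside the planned one. The Part 1 coupling-ratio model in the SAP needs no change for this point.

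The cost is one model term built from the recorded visit number and one degree of freedom. If there is no period effect, power at 15 participants falls from 84% to 83% with a 7:8 split, or to 79% under simple randomisation; blocking avoids most of that loss. At 40 with equal sequences the confidence interval widens by about 0.1%.

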H3.1: When walking in a straight line, the peak transverse-plane moment will be significantly different between the Pivot-Flex Foot and the standard-of-care prosthesis.

H3.2: When circle walking with the prosthetic limb on the inside of the turn, the peak transverse-plane moment will be significantly different between the Pivot-Flex Foot and the standard-of-care prosthesis.

H3.3: When circle walking with the prosthetic limb on the outside of the turn, the peak transverse-plane moment will be significantly different between the Pivot-Flex Foot and the standard-of-care prosthesis.

H4.1: When walking in a straight line, the positive sagittal-plane work done at the hip joint will be significantly different between the Pivot-Flex Foot and the standard-of-care prosthesis.

H4.2: When circle walking (steady-state turning) with the prosthetic limb on the inside of the turn, the positive sagittal-plane work done at the hip joint will be significantly different between the Pivot-Flex Foot and the standard-of-care prosthesis.

H4.3: When circle walking (steady-state turning) with the prosthetic limb on the outside of the turn, the positive sagittal-plane work done at the hip joint will be significantly different between the Pivot-Flex Foot and the standard-of-care prosthesis.

Our interest in the positive sagittal-plane work done at the hip joint stems from the lack of propulsive power produced by passive prosthetic feet during ambulation by individuals with lower limb amputation. While energy storing and returning prosthetic feet can provide some propulsive assistance, the positive sagittal-plane ankle joint power and work produced is far below that provided by the ankle-foot musculature of the intact limb (e.g., [56, 57]).

Individuals with lower limb amputation compensate with greater sagittal-plane hip joint power and work, which is likely one of the reasons why they walk slower and at higher metabolic cost than their intact counterparts (e.g., [17, 58-60]). Our preliminary results with the TAP suggest that when the coupling ratio was increased: (1) prosthetic-side positive hip work may decrease during straight walking and prosthesis-on-the-outside during circle walking, and (2) prosthetic-side negative hip work may decrease during prosthesis-on-the-outside during circle walking. Both are desirable outcomes as they may reduce the biomechanical effort associated with walking.

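### Aim 2: Holm would give the same 5% experiment-wise control as the planned Bonferroni over six foot contrasts and can only reject more; a free improvement, not an error

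*Protocol*

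**What the plan says.** The Specific Aim 2 part of Protocol section 5.6 lists H3.1–H3.3 (peak transverse-plane moment) and H4.1–H4.3 (positive sagittal-plane hip work). Each outcome is tested in straight walking and in circle walking with the prosthesis on the inside and on the outside. The hypotheses are two-sided; for H3, for example, "the peak transverse-plane moment will be significantly different between the Pivot-Flex Foot and the standard-of-care prosthesis". Testing them "will require six linear mixed effects regression analyses", each with foot type at two levels.

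On multiplicity, the section fixes an experiment-wise 0.05 and adds that "a Bonferroni adjustment will be applied for multiple comparisons". It prints no divisor and names no step-down method. It promises exact p-values and does not mention confidence intervals.

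The SAP covers only the coupling-ratio analysis of Part 1, with Tukey's adjustment for pairwise comparisons. The protocol paragraph is therefore the only multiplicity rule for Part 2.

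**The concern.** Each Aim 2 model contains one comparison, so there is nothing to adjust within a model. The natural family for an experiment-wise level is the six hypotheses, each tested at 0.05/6. Single-step Bonferroni holds every test to that threshold, even after others have been rejected. Holm starts at 0.05/6 for the smallest p-value and relaxes to 0.05/5, 0.05/4 and so on as hypotheses are rejected. It needs no assumption about how the outcomes are correlated.

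What is at stake is power on the device comparison. The difference between the methods grows with the number of real effects, and section 3.0 hopes for effects on both socket torque and compensatory gait.

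**Working it through.** **Inputs.** From the Aim 2 power paragraph in section 5.6: "peak ankle rotational torque of 0.167 ± 0.011 Nm/kg for the inside limb", measured in able-bodied subjects in the cited turning study; "Assuming a 10% within-subject difference between study prostheses"; standard deviations like those of that study; 15 participants; stated power over 97%. The SD of the within-subject difference is not given. I assume zero correlation between feet, because that reproduces the stated power.

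**Reproducing the plan's figure** (two-sided paired t-test, 14 df):
- Difference: 0.10 × 0.167 = 0.0167 Nm/kg.
- SD of the difference: √2 × 0.011 = 0.01556.
- Noncentrality: 0.0167 / (0.01556/√15) = 4.158.
- Power at unadjusted 0.05: 97.1%, which matches the stated figure.

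**At the planned Bonferroni level.** 0.05/6 = 0.00833, and the same noncentrality gives 83.9% per hypothesis.

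**Holm.** Order the p-values and reject the k-th smallest while p(k) ≤ 0.05/(6 − k + 1), stopping at the first failure. Any p-value at or below 0.05/6 passes every step up to its own, so Holm rejects everything Bonferroni rejects. I simulated six paired t-tests at n = 15 with equal correlation between outcomes, giving every real effect the size above. Mean power per real effect:

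| Real effects | Bonferroni | Holm, correlation 0 | Holm, correlation 0.5 |
|---|---|---|---|
| 1 | 84% | 84.1% | 84.0% |
| 3 | 84% | 87.6% | 87.1% |
| 5 | 84% | 92.6% | 91.1% |
| 6 | 84% | 95.9% | 93.6% |

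At correlation 0.8, Holm gives 89.8% with five real effects and 91.5% with six. With all six real, the chance of rejecting all six rises from 35% to 82% (correlation 0) or from 52% to 85% (correlation 0.5). In no replicate did Bonferroni reject a hypothesis that Holm kept.

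**Error control.** The largest simulated familywise error with Holm was about 4.9%. It occurred with no real effects and independent outcomes, where theory gives 1 − (1 − 0.05/6)^6 = 4.9% for both methods. With five real effects and independent outcomes, the realised error on the remaining null was 0.9% with Bonferroni and 4.3% with Holm.

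**Sensitivity of the Bonferroni figure on the same inputs.**
- n = 20: 95.6%. n = 25: 99.0%. n = 40: noncentrality 0.0167 / (0.01556/√40) = 6.790, power 99.99%.
- n = 15 with SD of the difference 0.011 (correlation 0.5 between feet): 99.3%.
- H3 and H4 treated as separate families of three (0.05/3), n = 15: 90.7%.

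**The case against.** Bonferroni is a valid choice and the plan contains no defect here. A reader might infer that the multiplicity rule is wrong; it is not, and the point concerns efficiency only.

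A reader might also infer that the trial gives up 12 points of power (84% to 96%) on its own inputs. The documents do not support that. The top figure needs all six effects to be real, of equal standardized size, and independent. The plan gives inputs only for the peak moment on the inside limb and none for hip work. All outcomes come from the same participants, so some correlation is likely. The preliminary results in section 5.6 suggest less positive hip work in straight walking and with the prosthesis on the outside, but report no such decrease for the inside turn. If only the three moment hypotheses have real effects, the gain is 3 to 4 points.

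Enrolment matters too. Section 5.1 targets 40 for Part 2, and there the gain disappears on these inputs. One could restore it by pairing the 17% SD from the Aim 1 power paragraph with Aim 2's 10% difference: at n = 40 Bonferroni then gives 82%, and Holm 91–93% if all six effects are real. But that SD comes from one participant comparing coupling ratios, and the protocol pairs it with a 19% difference. The combination shows sensitivity to larger variability; it is not a planning figure of this trial.

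Three further objections stand in part. The divisor of six is inferred, and section 3.0 lists H3 and H4 as separate general hypotheses. Bonferroni also bounds the expected number of false rejections at 0.05, which Holm does not (0.061 in one all-null simulation at correlation 0.8). And Bonferroni has simple matching simultaneous intervals, which Holm lacks, although this section promises only p-values.

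None of this touches the main result: at the same familywise guarantee, Holm cannot reject fewer hypotheses.

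**Conclusion.** This is a free improvement, not a correction of an error. For the six Aim 2 tests Holm keeps the experiment-wise 5% under any dependence and rejects at least what Bonferroni rejects. That holds whatever the power inputs.

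The size of the benefit does depend on them. At 15 participants it runs from practically nothing with one real effect to between 7 and 12 points with six. This rests on the peak-moment inputs applying to every real effect, zero between-foot correlation, and a family of six. At 40 participants on the same inputs it is negligible. It would remain at that size only if variability in amputee participants is much larger than the able-bodied SD. The protocol describes enrolment as up to 40 and bases its power statement on 15, so the smaller sample is worth protecting.

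**What to change.** In the Aim 2 analysis paragraph of Protocol section 5.6, name Holm in place of Bonferroni. State that the family is the six tests H3.1–H3.3 and H4.1–H4.3. Report Holm-adjusted p-values beside the exact ones. Carry the same sentence into the SAP, which at present has no Part 2 analysis. Make the change before Part 2 outcomes are examined, so that the choice cannot depend on the results.

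The cost is one word and a statement of the family in the plan, and one argument when the six p-values are adjusted in R. No participants, visits or data are added. In exchange, there are no simple matching simultaneous intervals, and the realised familywise error lies nearer to 5% when some effects are real.

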5.6 Data Analysis

Specific Aim 1: Kinematic and kinetic data from the experiment will be analyzed to identify the peak transverse-plane moment of the straight and both directions of the circle walking trials at the five different coupling ratios (0, 1:6, 1:4, 1:3, and 1:2). This data will be processed (Visual3D; C-Motion, Germantown, MD) and aggregated using project specific software (Matlab; Mathworks, Natick, MA).

We hypothesize that:

H1.1: When walking in a straight line, there exists a coupling ratio that minimizes the peak transverse-plane moment.

H1.2: When circle walking with the prosthetic limb on the inside of the turn, there exists a coupling ratio that minimizes the peak transverse-plane moment.

H1.3: When circle walking with the prosthetic limb on the outside of the turn, there exists a coupling ratio that minimizes the peak transverse-plane moment.

The statistical analysis to test these hypotheses (H1.1, H1.2, and H1.3) will require three linear mixed effects regression analyses. These analyses will test for differences between the five coupling ratios across the three different ambulatory activities with random effects for subject and subject by coupling ratio interaction. The experiment-wise significance will be set a priori at an alpha level of $p<0.05$ and a Bonferroni adjustment will be applied for multiple comparisons. All analyses will be performed using existing software (R Foundation for Statistical Computing with lme4 and multcomp packages, Vienna, Austria). Exact p-values will be reported for each test.

We conducted an exploratory power analysis for hypothesis **H1.1:** The peak torque at the interface between the socket and the residual limb will be significantly different between a passive prosthesis that couples transverse-plane rotation with ankle dorsiflexion and the standardized study prosthesis. For this within-subject randomized crossover study design, we used recently analyzed data ($n=1$) to compare the effect of a coupling ratio of 0 with 1:2. The difference in peak socket torque was 19% between the two coupling ratios with a standard deviation of 17% between peaks. We calculated 98 percent power to find a significant difference between the test prostheses at $p<0.05$ for 15 subjects.

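### The Part 2 power of over 97% shows no allowance for the planned Bonferroni adjustment and rests on an able-bodied ankle-torque SD that the protocol does not justify for amputee socket torque

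*Protocol*

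**What the plan says.** The Part 2 power paragraph closes section 5.6 of the protocol (Data Analysis, Specific Aim 2). It is labelled exploratory. It takes peak torque values "exerted by able bodied subjects performing a turning task", from a cited study of 10 people, "with a peak ankle rotational torque of 0.167 ± 0.011 Nm/kg for the inside limb". It continues: "Assuming a 10% within-subject difference between study prostheses", and supposing SDs like those of the cited study, "there is over a 97% chance to find a significant difference between stiffness settings for 15 participants".

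The Aim 2 hypotheses concern socket torque in people with transtibial amputation (section 3.0, H3). For each of three walking tasks, section 5.6 says that "the peak transverse-plane moment will be significantly different between the Pivot-Flex Foot and the standard-of-care prosthesis". Three parallel hypotheses concern hip work, which makes six mixed models. On error control it says: "The experiment-wise significance will be set a priori at an alpha level of $p<0.05$ and a Bonferroni adjustment will be applied for multiple comparisons". It does not say how many tests make up the family.

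The Part 1 power statement, for H1.1 (straight walking) in the same section, uses different variability data: "we used recently analyzed data ($n=1$) to compare the effect of a coupling ratio of 0 with 1:2". It reports: "The difference in peak socket torque was 19% between the two coupling ratios with a standard deviation of 17% between peaks". From this it derives 98% power with 15 subjects.

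Section 5.1 gives a targeted enrolment of 40 for Part 2. The SAP models outcomes by coupling ratio only, so it does not settle the Part 2 family size or power.

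**The concern.** There are two separate problems with the one figure.

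**Alpha.** The power paragraph shows no multiplicity allowance, while the analysis paragraph just before it promises one. If the figure was computed at 0.05, it describes a more lenient test than the one planned.

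**SD.** The calculation borrows spread from another population (able-bodied), another quantity (ankle torque) and a single task (the inside limb in a turn). No reason is given why that spread should hold for torque at an amputee's socket. The one socket-torque figure in the protocol is 17/6.59 = 2.6 times larger, and the protocol does not discuss the difference. The text also does not say whether either SD is per condition or of the paired difference. For a crossover comparison that choice drives the answer.

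This is the only sample-size justification offered for Part 2. A non-significant result in 15 people, read against a stated power above 97%, would look like strong evidence that the Pivot-Flex Foot does not change torque by 10%. That inference is only as sound as the SD and the alpha behind it.

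**Working it through.** **Inputs (protocol section 5.6).** Mean 0.167 and SD 0.011 Nm/kg, so SD/mean = 0.011/0.167 = 6.59%. Difference 10% of the mean. n = 15. Two-sided testing is assumed because the hypotheses are non-directional. Part 1: difference 19%, SD 17%, n = 15.

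**Method.** Exact paired t-test power from the noncentral t distribution: df = n - 1, noncentrality = (difference / SD of difference) x sqrt(n). For a per-condition SD s and correlation r, SD of difference = s x sqrt(2(1 - r)).

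**1. Reproduce the Part 2 figure.** With r = 0, SD of difference = 6.59 x sqrt(2) = 9.32%. Noncentrality = (10/9.32) x sqrt(15) = 4.16. At two-sided 0.05, power = 97.1%, matching the statement. Other readings give 98.0% (two-sample t, 15 per condition), 98.6% (normal approximation) and 99.98% (6.59% as the SD of the difference). All are literally over 97%, but only the first lands on 97.

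**2. Apply the planned Bonferroni adjustment to those inputs.**
- Three tests (H3 only), alpha 0.05/3: 90.7%.
- Six tests (H3 and H4), alpha 0.05/6: 83.9%.

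**3. Reproduce the Part 1 figure.** With 17% as the SD of the paired difference, noncentrality = (19/17) x sqrt(15) = 4.33 and power = 98.0%, matching the stated 98%. With 17 x sqrt(2) it would be 81.2%. So Part 1 appears to treat its SD as that of the difference, and Part 2 appears to treat its SD as per condition.

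**4. Sensitivity of Part 2 to the 17% figure (10% difference, n = 15).**

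| What the 17% is taken to be | SD of difference | Power at 0.05 | Power at 0.05/6 |
|---|---|---|---|
| SD of the paired difference (Part 1 convention) | 17.0% | 56.4% | 26.2% |
| Per-condition SD, r = 0 (Part 2 convention) | 24.0% | 32.3% | 11.1% |
| Per-condition SD, r = 0.7 | 13.2% | 78.1% | 47.6% |
| Per-condition SD, r = 0.8 | 10.8% | 91.7% | 69.6% |
| Step-to-step spread, 3 passes averaged | 17 x sqrt(2/3) = 13.9% | 73.7% | 42.4% |
| Step-to-step spread, 6 passes averaged | 17 x sqrt(2/6) = 9.8% | 95.6% | 79.1% |

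The correlations are assumptions; the documents give none. The 3 to 6 passes come from section 5.5. The last two rows assume that the foot effect does not vary between subjects, although the Part 2 model includes a subject-by-foot-type random effect. Any such variation lowers them.

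**5. Threshold.** For 97% power at n = 15 and 0.05, the SD of the difference must not exceed about 9.35% of the mean. The reproduced calculation sits at 9.32%, so it has almost no slack.

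**6. Targeted enrolment.** At n = 40 with SD of difference 17%, power is 95.2% at 0.05 and 82.0% at 0.05/6. With 17 x sqrt(2) it is 72.8% at 0.05.

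**The case against.** The strongest reply is that the 17% cannot carry much weight. It comes from one subject, on the motorised device, for the straight-walking hypothesis, and it is described as spread between peaks. One person cannot supply an SD of paired differences across people; the figure may be step-to-step spread within that person. The 6.6% comes from 10 people in a turn. Task, device and probably variance component all differ, so the two figures need not contradict each other. This stands. A reader might infer that the true Part 2 power is 56% or less; the documents do not support that as an upper bound, because other admissible readings reach 78% to 96%.

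A reader might also infer a calculation error. There is none: 97.1% follows from plausible readings of the stated inputs. The problem is an unsupported assumption together with an alpha that does not match the plan.

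On the alpha, the convention is inferred rather than documented. If 0.011 is the SD of the paired difference, power at 0.05/6 is still 99.3%. So the loss to 90.7% or 83.9% applies to the reading that matches the stated figure, not to every reading. A family of six is not documented either; three is equally possible.

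The paragraph also calls itself exploratory, discloses its able-bodied source and makes its result conditional on similar SDs. Those are fair disclosures, but they neither justify the SD nor bring the alpha into line with the analysis paragraph.

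Finally, a reader might infer that Part 2 as a whole is underpowered. The stated power is for 15, whereas targeted enrolment is 40, where even an SD of difference of 17% leaves 82% at 0.05/6. The shortfall belongs to the claim for 15.

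**Conclusion.** The concern holds in a limited form. On the inputs and convention that best reproduce the stated figure, the planned Bonferroni adjustment takes power for 15 participants from 97.1% to 90.7% (three tests) or 83.9% (six). This result does not depend on the 17%.

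Separately, nothing in the protocol supports applying the 6.6% SD to amputee socket torque. The only socket-torque figure it contains, weak as it is, puts power for 15 participants anywhere from 32% to 96% at 0.05. The reading consistent with Part 1 gives 56%. None of the readings in the table reaches 97%, but the documents do not fix which of them is right.

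These figures assume a two-sided paired t-test as a stand-in for the mixed model, complete data, and a true difference of exactly 10%.

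**What to change.** In the Part 2 power paragraph of section 5.6:

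- Compute power at the Bonferroni-adjusted alpha and name the number of tests in the family.
- State whether the SD is per condition or of the paired difference, and use the same convention as Part 1. If it is per condition, give the assumed correlation.
- Replace the single figure with power for 15 and for the targeted 40 participants over an SD range of 6.6% to 17%. Better still, use the SD of paired differences from completed Part 1 data, if available.
- Say why the able-bodied value is kept, if it is.

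The cost is wording and a less favourable stated figure. No additional enrolment and no design change are requested.
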